PECS/SAP blocks with liposomal bupivacaine improve the Overall Benefit Analgesia Score averaged over the postoperative days 1, 2, and 3. A 20% reduction in OBAS geometric mean, a-priori, was defined as minimal clinically important difference.

Secondary hypotheses:

- (1) PECS/SAP blocks decrease postoperative cumulative opioid consumption over the initial three postoperative days.
- (2) PECS/SAP blocks improve pulmonary mechanics, on each of the postoperative days 1, 2 and 3, from the baseline.

Exploratory Hypothesis:

- (1) PECS/SAP blocks improve the Quality-of-Recovery score averaged over the postoperative days 1 and 3, with a difference of 8 points being considered the minimum clinically important difference.⁵⁴
- (2) PECSII and SAP blocks reduce persistent postoperative surgical pain

Methods

The study will be conducted at the Cleveland Clinic Main Campus with IRB approval and written informed consent from participating patients.

Inclusion Criteria

1. 18-85 years old;
2. Elective MICS for isolated robotically-assisted mitral valve repair via anterolateral thoracotomy approach.

Exclusion Criteria

1. Weight less than 50 kg;
2. Pregnancy or lactation;
3. Emergency surgery and patients transferred from the ICU to the operating room;
4. Redo cardiothoracic surgery or post-operative reoperation within 72 hours of index procedure (including minor chest wall procedures including tube thoracostomy, thoracentesis or percutaneous drain placement);
5. Anticipated endotracheal intubation > 24 hours;
6. Anticipated non-study nerve block that provides analgesia to the intercostal nerves;
7. Active systemic or cardiopulmonary infection;
8. Mechanical circulatory support;
9. Allergy or contraindication to study local anesthetics;
10. Current chronic pain or routine opioid use (patients on chronic enteral opioids like Percocet or Vicodin) in a dose of > 30 mg of morphine-milligram-equivalents for at least 10 days in last 30 days;
11. Poorly controlled psychiatric disorders;
12. Clinically important current neurologic deficit; e.g. spinal cord injury, paralysis of extremity, any neurologic deficit in the region of the block
13. Active liver disease or cirrhosis;
14. Pacemaker generator or breast implants ipsilateral to surgery;
15. Previous participation in this study.
16. eGFR <30 or chronic kidney disease

Study protocol

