Pain scores on a 0-10 verbal response scale will be evaluated, per routine, by the nursing staff every four hours while patients remain hospitalized. Pain scores (0-10) will be recorded along with the OBAS measurements at rest and then after provocation in the form of a vigorous coughing.

Total opioid consumption as well as intraoperative and postoperative day 1, 2, and 3 totals will be collected and converted to milligram morphine equivalents (Table 4). Patients will not be given opioid patches because there is no known conversion to morphine equivalents.

c) FEV₁, FVC and peak flow

FEV₁, FVC and peak flow will be recorded preoperatively at baseline and at bedside, on the first postoperative mornings 1, 2 and 3. The FEV₁, FVC and peak flows will be measured using Easy on-PC Spirometry System (ndd Medical, Andover MA) with the patient in the sitting position. The measurements and will be obtained by the qualified research personnel and interpreted by the staff pulmonologist. The average of three tests will be considered to be the final result.

d) Quality-of-Recovery-15 (QoR-15) score

The QoR-15 is a quality of recovery score that provides a patient-centered global measure of overall health status after surgery and anesthesia. It comprises 15-item questionnaire with range of responses from 0-150 (<http://links.lww.com/ALN/B274>). The patients will be given a questionnaire on the first and the third postoperative days, the response collected and the difference from the previous days calculated. Myles et al. reported a minimal clinically important difference in the QoR-15 score of 8 which will be used in this study.⁵⁴

e) Pharmacokinetic (PK) Sample Collection

Blood samples (4 mL each) will be collected from 16 subjects from the treatment group in order to determine pharmacokinetic parameters of liposomal bupivacaine. These samples will be collected at the following time stamps after the injection of the liposomal bupivacaine through PECS/SAP blocks: 15±5 min, 30±5 min, 1h±5 min, 4h±10 min, 24h±20 min, 32h±20 min, 40h±20 min, 48h±20 min, 72h±20 min, 84h±20. The samples will be obtained from a dedicated IV line in a separate location or from an arterial line.

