The Blood samples will be collected into K2EDTA tubes and will be centrifuged at 1000 to 1200g for 10 min to obtain plasma within 1 hour of collection. After centrifugation, the plasma will be transferred into polypropylene tubes. The plasma samples will be stored frozen at -20°C or colder until shipment. All samples will be shipped frozen with dry ice to ABS Laboratories, Inc. The shipment address is as follows: [name] ABS Laboratories, Ltd. [name]

Descriptive and Safety Outcomes

- a) Total ICU length of stay;
- b) Hospital length of stay;
- c) Cumulative non-opioid analgesics included acetaminophen, ketorolac, ibuprofen, gabapentin, and pregabalin will be recorded and compared over the initial three postoperative days;
- d) Anxiolytics such as alprazolam, lorazepam, and diazepam will be recorded and compared.

Statistical analysis

We will compare groups on potentially confounding demographic and preoperative risk factors listed in Table 1 using appropriate summary statistics (i.e., mean ± standard deviation, median [Q1, Q3], or N (%) as appropriate) as well as surgical and intraoperative data will be collected prospectively (Table 2). Randomized groups will be compared on balance on these characteristics using absolute standardized difference, defined as the absolute difference in means, mean ranks, or proportions divided by the pooled standard deviation.

Analyses will be modified intent-to-treat, including all randomized patients who received PECSII/serratus blocks (regardless of whether it's consistent with the randomization).

We will summarize descriptive and safety outcomes by randomized groups using appropriate summary statistics (i.e., mean \pm standard deviation, median [Q1, Q3], or N (%) as appropriate). No statistical tests will be performed on these outcomes.

We will use an alpha of 0.05 for both the primary and secondary analyses, with a significance criterion of 0.05 for the primary analysis and 0.0167 for each secondary analysis (i.e., 0.05/3, Bonferroni correction). Analyses will be completed using SAS version 9.4 or newer (SAS Institute, Carey, North Carolina) or R version 3.2.4 or newer (R Project for Statistical Computing, Vienna, Austria).

Primary analysis

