We will estimate the PECS/SAP blocks effect on OBAS scores using a repeated measures linear regression model with an autoregressive correlation structure, adjusting for ALL imbalanced confounders (if any). Based on these model we would be able to claim if the PECS/SAP blocks had any effect on the OBAS score compared to standard routine analgesia during any of the postoperative time up to third postoperative day. Due to non-normality of OBAS score, it will be log-transformed for analysis. We will report model based P-value and the geometric mean ratio for OBAS scores along with confidence intervals. To assess whether the PECS/SAP blocks effect is heterogeneous over three postop days, we will assess the treatment-by-time interaction using a significance criterion of 0.20. If it appears that the treatment effect is heterogeneous, we will report the treatment effect separately for each postoperative day POD 1, POD 2 and POD 3 using a Bonferroni correction as appropriate (e.g., 0.05/3; 3 postoperative days).

Secondary Analysis

Morphine equivalents will be calculated based on the conversions specified in Table 4 below. Total opioid consumption as well as intraoperative and postoperative day 1, 2, and 3 totals will be collected and converted to milligram morphine equivalents. Patients will not be provided opioid patches for pain relief because there is no known conversion to morphine equivalents. Cumulative opioid consumption data is typically right skewed, so we will normalize it for analyses using a log transformation. Opioid consumption will be reported separately for postoperative day (POD) 0 after surgery, POD 1, POD2, and POD3. We will estimate the effect of PECS/SAP blocks to standard routine analgesia on log cumulative opioid consumption using a repeated measures linear regression model with an autoregressive correlation structure, adjusting for any imbalanced baseline or surgical characteristics between groups.

To assess whether the effect of PECS/SAP blocks is heterogeneous over time, we will assess the treatment-by-time interaction using a significance criterion of 0.20. If it appears that the treatment effect is heterogeneous, we will report the treatment effect separately for each postoperative day using a Bonferroni correction as appropriate (e.g., 0.05/3; 3 postoperative days).

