We will estimate the effect of PECS/SAP blocks on FEV_1 , FVC and peak flow rate using three separate repeated measures regression models with an autoregressive correlation structure, adjusting for baseline FEV_1 , FVC, peak flow rate and imbalanced confounders (if any).

The Wald tests for regression model coefficients will be used to test each of the secondary hypotheses; the Bonferroni correction for four outcomes will be employed to control the overall Type I error rate at 0.05 for the secondary outcomes.

Exploratory Analysis

Two separate linear regression models will be developed to assess the relationship between analgesia strategy and each of the two exploratory outcomes (quality of recovery after anesthesia survey and persistent postoperative surgical pain). To compare patients from two groups on these outcomes mean difference will be reported along with 95% confidence intervals.

Descriptive and Safety Analyses

We will summarize descriptive and safety outcomes by randomized groups using appropriate summary statistics (i.e., mean \pm standard deviation, median [Q1, Q3], or N (%) as appropriate). No statistical tests will be performed on these outcomes.

Sample Size Considerations

Per Mamoun, observed a coefficient of variation (CV) of 53% in the placebo group of cardiac surgery patients.⁵⁹ We assumed a slightly more conservative CV of 50% and that the treatment effect favored PECS/SAP blocks by 20% (i.e., true ratio of geometric means of 0.80). We will need to enroll approximately 192 patients (96 per group) to have 90% power at the 0.05 significance level to detect superiority of PECS/SAP blocks to standard routine parenteral and enteral analgesia in patients recovering from MICS .

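### Secondary hypothesis (2) claims better lung function on each of POD 1, 2 and 3, but the analysis as written appears to give each lung measure one overall test and states no rule for a daily claim

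*Combined protocol and SAP*

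**What the plan says.** Under Secondary hypotheses, item (2) states: "PECS/SAP blocks improve pulmonary mechanics, on each of the postoperative days 1, 2 and 3, from the baseline". The primary hypothesis, just above it, is framed differently: the blocks "improve the Overall Benefit Analgesia Score averaged over the postoperative days 1, 2, and 3". The opioid hypothesis is cumulative over three days, and the exploratory quality-of-recovery hypothesis is again an average. Only lung function is worded day by day.

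Study Measurements, item (c), has FEV1, FVC and peak flow "recorded preoperatively at baseline and at bedside, on the first postoperative mornings 1, 2 and 3".

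The Secondary Analysis section plans "three separate repeated measures regression models with an autoregressive correlation structure", adjusted for baseline and any imbalanced confounders. It continues: "The Wald tests for regression model coefficients will be used to test each of the secondary hypotheses", and "the Bonferroni correction for four outcomes will be employed to control the overall Type I error rate at 0.05 for the secondary outcomes". The general Statistical analysis section gives a different threshold: "0.0167 for each secondary analysis (i.e., 0.05/3, Bonferroni correction".

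After the opioid model, and before the lung-function models are introduced, a separate paragraph says: "To assess whether the effect of PECS/SAP blocks is heterogeneous over time, we will assess the treatment-by-time interaction using a significance criterion of 0.20". If heterogeneity appears, effects are reported by day with a Bonferroni correction. The paragraph names no outcome.

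**The concern.** Improvement on each of three days is a conjunction: all three daily effects must be present. A single treatment coefficient in a repeated measures model estimates a weighted average of the daily effects. It can be significant when one day carries the whole effect, and it does not show that every day contributes.

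The four outcomes in the correction are opioid consumption and the three lung measures, which leaves one test per measure. If so, the plan can be followed exactly without testing hypothesis (2) as worded. This touches three of the four secondary tests, and respiratory function is a stated part of the trial's rationale.

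**Working it through.** **The plan's own figure.** The only sample-size derivation concerns OBAS. With CV 50%, the log-scale SD is √ln(1.25) = 0.4724; with ratio 0.80, |ln 0.80| = 0.2231. Then 2 × [(1.960 + 1.282) × 0.4724 / 0.2231]² ≈ 94.2, so 95 per group against the stated 96. Inflating by the Table A drift gives 192 × (3.26890 / 3.2415)² = 195.3, against the stated 196. The figure reproduces, and this point does not touch it.

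**Inputs.** From the documents: n = 98 per group, three postoperative measurements, autoregressive correlation, alpha 0.05/4 = 0.0125 (two-sided z = 2.498). Assumed, because the documents are silent: correlation ρ = 0.5–0.6 and effects in units of the residual SD.

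**Formulas.** SE of one day's difference: √(2/98) = 0.1429.

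- Common (GLS) coefficient: day weights (1, 1−ρ, 1)/(3−ρ), variance (2/n)(1+ρ)/(3−ρ). At ρ = 0.5 the weights are 0.40, 0.20, 0.40 and the SE is 0.1107; at ρ = 0.6 they are 0.417, 0.167, 0.417 and the SE is 0.1166.
- Equal-weight average: variance (2/n)(3 + 4ρ + 2ρ²)/9, so the SE is 0.1117 at ρ = 0.5 and 0.1178 at ρ = 0.6.
- Probability of significance in favour of the block: Φ(weighted effect / SE − 2.498).

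Example (0.8 SD on POD 1 only, ρ = 0.5, GLS): 0.40 × 0.8 / 0.1107 = 2.89, and Φ(2.89 − 2.498) = 0.65.

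| Effect on POD 1 only | GLS coefficient significant | Equal-weight average significant |
|---|---|---|
| 0.4 SD | 14–15% | 9–10% |
| 0.6 SD | 36–37% | 21–24% |
| 0.8 SD | 64–65% | 41–46% |

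In each row, all three daily contrasts pass at 0.0125 in about 0.1% of trials.

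**Sensitivity.** An effect of 0.8 SD on POD 2 only gives 9–15% for GLS, because the middle day has little weight, and 41–46% for the equal-weight average. A waning effect of 0.6, 0.3 and 0 SD gives 53–58% for GLS, with all three days passing in about 0.6%. At alpha 0.0167, the 0.8 SD POD 1 case gives 68–69% for GLS.

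**If the 0.20 interaction step does apply to lung function.** For an effect δ on POD 1 only, the 2-df test has noncentrality (n/2)δ²[1/(1−ρ²) − 1/((1+ρ)(3−ρ))]. At 0.4 SD this is 8.4 (ρ = 0.5) or 10.2 (ρ = 0.6), so the interaction is flagged in 91–95% of trials. At 0.6 SD it is flagged in 99.7–99.9%, and at 0.8 SD in more than 99.9%.

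**Cost of an all-days rule.** With a constant 0.4 SD on every day, all three contrasts pass at 0.0125 in 35–38% of trials, against 82–87% for the GLS coefficient and 82–86% for the equal-weight average.

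**The case against.** Four arguments on the other side carry weight.

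- **The single coefficient is an inference.** The plan does not list the model terms and speaks of coefficients in the plural. A reader might infer that the lung models definitely omit treatment-by-day; the text does not establish that. The four-outcome count supports one test per measure. If daily coefficients were intended, the plan still does not say which are tested or how they combine.
- **The interaction paragraph may cover lung function.** It names no outcome, and its example of three postoperative days fits spirometry at least as well as opioid use, which is reported for POD 0 to 3. Its position points to the opioid model. If it does apply, most POD 1-only effects of the sizes above would be flagged and reported by day. What remains is the unflagged case: failing to detect heterogeneity does not show an effect on each day, and no rule ties daily results to the hypothesis.
- **An early-only effect is not the documents' expectation.** A reader might take the bupivacaine HCl duration of under 12 hours as making it likely. The same Local anesthetic section adds liposomal bupivacaine for that reason, and the Introduction states analgesia of up to 72 h. Blocks are normally placed before incision, so the short-acting component may have worn off by the first postoperative morning.
- **A significant average is a valid result.** Harm arises only if it is then reported as a daily one. The Aims section speaks neutrally of evaluating mechanics on POD 1, 2 and 3, so the hypothesis wording may describe the measurement schedule. A reader might infer that a one-day effect would be reported as improvement on every day; the plan does not say so. It leaves that reading open.

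**Conclusion.** The mismatch stands as one of wording and specification. Hypothesis (2) is stated day by day, while the lung-function analysis appears to deliver one overall test per measure, with no daily contrast or decision rule written down. Whether the interaction step covers these models is unclear, and it would not close the gap when the interaction is not significant.

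The risk cannot be sized from the documents. The 14–65% range for a common coefficient assumes an effect confined to POD 1 of 0.4 to 0.8 SD, ρ of 0.5–0.6, 98 per group and alpha 0.0125. It is lower with equal weights, and lower for the GLS coefficient if only POD 2 is affected. The point concerns secondary outcomes and leaves the primary analysis and sample size untouched.

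**What to change.** 1. Reword hypothesis (2) as the effect averaged over POD 1–3, and test the equal-weight average contrast for each lung measure at the secondary alpha.
2. State that the treatment-by-day term also applies to the FEV1, FVC and peak-flow models. Report each day's baseline-adjusted difference with its CI, whether or not the interaction is flagged.
3. Allow a claim of improvement on each day only if all three daily contrasts pass at that outcome's alpha. Because all must pass, no further correction across days is needed.
4. Settle the secondary alpha at the same time. With four outcomes, 0.05/4 = 0.0125 keeps the total at 0.05, whereas 4 × 0.0167 = 0.067 exceeds it.

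The cost is a wording change and one model term in three models, with no new data. The all-days claim has much lower power (about 35–38% against 82–87% for the average under a constant 0.4 SD effect). It should therefore be an additional, stronger claim and not replace the averaged test.

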Additional amendment to this protocol

- 1- Twelve patients' surgery type was planned to be a minimally invasive surgery, however after the randomization, their surgery type has been converted to a sternotomy during their surgery. Because of this, these patients were not qualified for the study and their follow-ups couldn't be completed. To be able to keep the power of the study, we would like to add 12 more patients to our total enrollment number which was 196 before. Adding 12 more patients, 208 is proposed to be the total number.

Version 5: November 3, 2021

- We would like to add more patients per our statistical team suggestion to increase the power. Our total number approximately will be 214. (page 13)

Version 6: July 6, 2022

- The primary analysis method was revised due to non-normality of primary outcome from "We will report model based P-value and the difference in mean OBAS scores along with confidence intervals." as "Due to non-normality of OBAS score, it will be log-transformed for analysis. We will report model based P-value and the geometric mean ratio for OBAS scores along with confidence intervals."
- The smallest clinically important difference of 2 point reduction in OBAS score was corrected as 20% reduction in geometric means.
- One inclusion criteria was more clearly stated as "Elective MICS for isolated robotically-assisted mitral valve repair via anterolateral thoracotomy approach."
- Sample size was more clearly stated for consistency.

Introduction

Over the past several decades the popularity of minimally invasive cardiac surgery (MICS) increased consequent to advances in imaging, instrumentation, and surgical skills.^{1,2} An increase in the age-related prevalence of the valvular heart disease³ also prompted novel surgical approaches.⁴ In addition to non-inferior operative mortality, the intermediate and long-term survival results are comparable to the traditional median sternotomy approach for both mitral⁵⁻¹⁰ and aortic valve¹¹⁻¹⁴ procedures. The reported advantages are also seen in terms of decreased infection rate, shorter time to extubation and hospital length of stay, decreased postoperative bleeding and transfusion rate, improved cosmesis, better postoperative respiratory dynamics and patient's satisfaction.^{5-7,15,16}

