The PECS and SAP blocks are easy to perform, and have a high success rate with few complications, particularly when performed with ultrasound guidance. Unlike epidural and paravertebral blocks, PECS and serratus blocks do not cause a sympathectomy which facilitates their use in the hemodynamically compromised patients.³⁷ Because of the *superficial* nature of the blocks, the risk of pneumothorax is minimal, particularly with the in-plane ultrasound needle guidance.³⁷ The local anesthetic toxicity syndrome is not been reported and could easily be avoided with a dilution of the local anesthetic and standard precautions.³⁸ Indeed, compared to the intercostal, interpleural, or paravertebral techniques, pain control was achieved with much smaller LA doses which suggests that there was less intravascular absorption. Under the ultrasound guidance, the blocks can be easily to perform with the patients asleep, thus avoiding discomfort and multiple injections.

Liposomal bupivacaine (Exparel; bupivacaine liposome injectable suspension, Pacira Pharmaceuticals, Inc., Parsippany, NJ USA) is a prolonged-release formulation of the bupivacaine used for a single-shot infiltration of the surgical site. The advantage of the prolonged-release formulation is analgesia lasting up to 72 h which should improve analgesia after MICS. In a small retrospective study of robotically assisted cardiac endoscopic procedures, comparing incisional infiltration with bupivacaine vs liposomal bupivacaine, Balkhy et al. demonstrated lower pain scores, reduced opioid consumption, and less postoperative nausea and vomiting — although none of the differences were statistically significant.¹⁸ The Exparel formulation containing a mixture of bupivacaine HCL and liposomal bupivacaine has demonstrated acceptable tolerability and incidence of adverse events relative to its non-liposomal counterpart, mainly in infiltration during hemorrhoid surgery, bunionectomy, breast augmentation, knee arthroplasty, and inguinal hernia repair.³⁹ Liposomal bupivacaine is FDA approved for infiltrative field blocks, such as the transversus abdominis plane (TAP) block which is similar to PECS and SAP blocks.⁴⁰

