A decrease in pulmonary mechanics associated with respiratory complications is one of the leading causes of postcardiac surgical morbidity.⁴¹ Less invasive surgical approaches may decrease respiratory morbidity, particularly in already compromised patients.⁴² However, the benefits of MICS in terms of pulmonary morbidity remain unclear.^{20,22} Indeed, respiratory complications are directly related to the incisional pain consequent to thoracotomy, rib disarticulation, and muscle distortion. Epidural and paravertebral analgesia reduce pulmonary complications and infections, and improve respiratory mechanics in patients having thoracic surgery^{43,44} but are rarely used. Other analgesia modalities including intercostal blocks did not comparably preserve pulmonary mechanics or reduce respiratory complications compared to neuroaxial techniques.^{44,45}

A combination of the PECS and SAP blocks provide good analgesia for mastectomy,⁴⁶⁻⁴⁸ thoracotomy^{35,36,49-51} and multiple rib fractures.^{38,52} However, their use in cardiac surgery and their effects on postoperative pain control or pulmonary mechanics have yet to be reported.

PECS and SAP blocks seem likely to enhance postoperative recovery after minimally invasive cardiac surgery. Pain after minimally invasive cardiac surgery is worst over the initial few postoperative days and compromises respiratory function. PECS and SAP blocks with liposomal bupivacaine thus seems likely to promote good analgesia and improved respiratory function.

Aims of the study

Our primary aim is to determine whether a PECS/SAP block, using a mixture of bupivacaine and liposomal bupivacaine, provides superior recovery compared to routine parenteral and enteral analgesia in patients recovering from MICS. Our primary outcome will be the simple multi-dimensional quality assessment, Overall Benefit Analgesia Score (OBAS score).⁵³

Our secondary aims are to: 1) compare cumulative postoperative opioid consumption (pain medications administered over one-day periods quantified as morphine equivalents and provided by the EMR for the day of surgery and postoperative days 1, 2, and 3; 2) evaluate respiratory mechanics (forced expiratory volume in first minute (FEV₁), forced vital capacity (FVC) and peak flow) after extubation on the postoperative days 1, 2 and 3 while patients remain hospitalized

Primary hypothesis:

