Consent will be obtained at least a day before surgery. Patients will be randomized the day of surgery upon presentation to the operating room to either a *treatment group* (PECS/SAP blocks) or a *control group* (standard parenteral analgesia technique with or without incisional LA infiltration) using secure web-based randomization. Randomization will be stratified by aortic or mitral valve surgery, with random blocking in each case. The system will be accessed shortly

before surgery to conceal allocation as long as possible. Clinicians will not be blinded to the intervention, but all outcomes will be assessed by research personnel who are blinded to the group assignment.

Anesthetic and Surgical Management

Anesthetic care will be performed as usual for Cleveland Clinic cardiothoracic surgical procedures. This includes use of standard ASA monitors and may include the use of arterial or central venous pressure monitoring, trans-esophageal echocardiography, and lung isolation using a bronchial blocker or a double lumen endotracheal tube. Medication administration for induction and maintenance of anesthesia will also be consistent with usual care and will include intravenous opioids such as fentanyl and hydromorphone. Intravenous lidocaine will not be administered upon induction of anesthesia.

Pressure-control ventilation will be used with a tidal volume not exceeding 6-10 ml/kg ideal body weight during two- and one-lung ventilation. Fluids will be managed conservatively per routine. Patients not extubated at the end of the procedure will be sedated with propofol. Surgical procedures with the assistance of the cardio-pulmonary bypass will be performed in their usual manner. The general approach for the AV replacement will be via the right anterior thoracotomy in the 3rd intercostal space.⁴ The MV repair/replacement procedures will be approached via the right lateral thoracotomy inframammary incision in the 4th intercostal space in the mid-axillary line and augmented, as needed, with the stab incisions for the robotic ports.⁴

Chest Wall Analgesia

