The anatomic basis for chest wall analgesia has been described in detail previously.^{31-33,49} We describe the conduct of the blocks as used for MICS procedures at our institution. The patients randomized to the “blocks” will receive PECS II and serratus anterior for the MVR requiring antero-lateral thoracotomy and port incisions. The PECS/serratus blocks will be performed with the patient under the general anesthesia before incision. If proves impossible to perform blocks preoperatively because of surgical urgency, they will be done at end of surgery.

PECS II blocks:

Patients will be positioned supine, and prepped and draped in a sterile fashion. An ultrasound probe will be placed just below the clavicle in the mid-clavicular line.

For the PECS II block, the probe will be scanned inferiorly and laterally until the plane between the pectoralis minor and serratus muscle is identified. The serratus muscle can be clearly seen coursing over the ribs, while the intercostal muscles are seen in the interspaces between the ribs. Once the plane is identified the needle is again advanced in an “in-plane” fashion. Once the needle location is confirmed by normal saline hydro-dissection, a 20-30 ml of local anesthetic solution is administered into the space.

Serratus plane block:

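### Exclusion criterion 4 includes chest procedures that can occur only after randomization, inside the POD 1-3 outcome window, and the plan does not say how such patients are followed, analysed or reported

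*Combined protocol and SAP*

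**What the plan says.** Item 4 of the Exclusion Criteria joins two different things. The first is redo cardiothoracic surgery, which is known beforehand. The second is "post-operative reoperation within 72 hours of index procedure (including minor chest wall procedures including tube thoracostomy, thoracentesis or percutaneous drain placement".

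The timing of the other steps is clear:

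- **Allocation** (Study protocol): "Patients will be randomized the day of surgery upon presentation to the operating room".
- **Treatment** (Chest Wall Analgesia): "The PECS/serratus blocks will be performed with the patient under the general anesthesia before incision". The end of surgery is a fallback when urgency prevents this.
- **Primary outcome** (Primary hypothesis): the blocks are to "improve the Overall Benefit Analgesia Score averaged over the postoperative days 1, 2, and 3".
- **Secondary outcomes** (Secondary hypotheses): cumulative opioid use over the first three postoperative days, and "PECS/SAP blocks improve pulmonary mechanics, on each of the postoperative days 1, 2 and 3, from the baseline".

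The Study protocol section leaves clinicians unblinded and blinds the research staff who assess outcomes. The Statistical analysis section defines a modified intent-to-treat set in terms of randomized patients who received the blocks, whether or not this matched their allocation. It does not mention criterion 4. The Descriptive and Safety Outcomes are ICU and hospital stay, non-opioid analgesics and anxiolytics. The complications in Table 2 are pneumonia, prolonged ventilation and gastrointestinal events.

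**The concern.** An exclusion criterion should be decidable before allocation. This part of criterion 4 is not. It takes effect, if at all, in the same three days in which every primary and secondary outcome is measured.

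The events may also be related to treatment. The Introduction ties respiratory complications directly to incisional pain, which the block is meant to reduce. It also names pneumothorax as a block risk, although it says that "the risk of pneumothorax is minimal". Tube thoracostomy, thoracentesis and drain placement are ways of dealing with pleural problems of this kind. The clinicians who would ordinarily order them know the allocation. Blinded assessors do not help here, because the question is who remains to be assessed.

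If the rule is applied, the groups compared are no longer the groups randomized. The aim to "evaluate respiratory mechanics" could lose some of the patients whose lungs did worst. Reoperation, pneumothorax, effusion and chest drainage are absent from the safety outcomes and Table 2. The interim analyses, which are meant to look at safety among other things, would then not see these procedures.

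**Working it through.** **Timing.** The order is randomization, then normally the block, then incision, end of surgery, and the 72 hours after the index procedure. The last interval largely coincides with POD 1-3. The criterion cannot be read as a forecast: items 5 and 6 of the same list say that the event is anticipated, and item 4 does not.

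**Planned size, reproduced.** Inputs from Sample Size Considerations: CV 50%, ratio 0.80, 90% power, alpha 0.05 (two-sided).

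- Log SD = sqrt(ln(1 + 0.5²)) = 0.4724; |ln 0.80| = 0.2231.
- n per arm = 2 × (1.960 + 1.282)² × 0.4724² / 0.2231² = 94.2, so 95 (190 in total). The noncentral t gives 96 (192 in total), as stated.
- Inflation for interim looks from Table A: (3.26890 / 3.2415)² = 1.017. Then 192 × 1.017 = 195.3, so 196, as stated.

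**Effect on power.** The documents give no rate for these procedures, so the rates below are assumptions. Power is for the group-sequential design, simulated with the Table A boundaries.

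| Removed | Of 196: left, power | Of 214: left, power |
|---|---|---|
| 0% | 196, 0.907 | 214, 0.929 |
| 2% | 192, 0.901 | 210, 0.924 |
| 5% | 186, 0.892 | 203, 0.917 |
| 10% | 176, 0.876 | 193, 0.902 |

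The 214 is the approximate enrollment in the Version 5 change entry. It absorbs (214 − 196)/214 = 8.4% removal while leaving 196. Power is not the main issue.

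**Effect on the estimate.** Let fractions p_B (block) and p_C (control) be removed, and let removed patients have OBAS r times that of the others in their arm. An arm's full log mean exceeds its retained log mean by p × ln r. Removal therefore changes the log geometric mean ratio by −(p_B − p_C) × ln r. Only the difference in removal matters.

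- Difference 3 points, r = 1.5: 0.03 × 0.4055 = 0.0122, about 1.2%. A full-population ratio of 0.80 becomes 0.790 if more block patients are removed (0.80 / 1.0122), or 0.810 if more controls are (0.80 × 1.0122).
- Difference 5 points, r = 2: 0.05 × 0.6931 = 0.0347, about 3.4%. The ratio becomes 0.773 (0.80 / 1.0353) or 0.828 (0.80 × 1.0353).
- Equal removal: no shift.

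**Scale.** With the plan's CV and 98 per arm, the standard error of the log ratio is 0.4724 × sqrt(2/98) = 0.0675. The shifts are 0.0122/0.0675 = 0.18 and 0.0347/0.0675 = 0.51 standard errors, or about 0.2 and 0.5. This treats the CV as applying to one value per patient; the repeated-measures standard error could differ.

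**The case against.** **Removal is not stated.** A reader might infer that criterion 4 deletes these patients and that their complications vanish from the trial. No section says that follow-up stops or that they leave the analysis. The analysis-set sentence read literally keeps a block recipient who has a chest tube placed on POD 1. This stands, and it makes the safety loss conditional on removal. It does not settle the matter: the sentence gives controls no clear protection, no section keeps these patients in follow-up, and the procedures are not listed for recording elsewhere.

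**The sternotomy conversions are another matter.** The Version 4 change entry reports 12 randomized patients converted during surgery and says that "these patients were not qualified for the study and their follow-ups couldn't be completed". It is tempting to use 12/196 = 6.1% as the size of this problem. The documents do not support that. The trigger was a change of operation, and no criterion 4 event is reported. The entry shows only that randomized patients have been disqualified, and replacements added, for an event after allocation.

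**A block pneumothorax may not reach the criterion.** The block is placed on the operative side before a thoracotomy, and the Introduction mentions chest tube placement with that approach. A needle injury might often be dealt with by the operation and its drains. It is therefore not shown that a block complication would commonly remove its own evidence. Drain removal times are not given, so later events remain possible.

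**The OBAS multiplier has no source.** Only one of the seven items in Table 3 rates pain directly, for at most 4 of 28 points. A factor of 1.5 to 2 in removed patients is an assumption.

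**Another reading of the wording.** The phrase could mean that the planned operation is itself a reoperation soon after an earlier one. This is less natural, since redo surgery is already named and the text says post-operative.

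**Conclusion.** As written, criterion 4 contains a condition that can be met only after randomization, and it conflicts with an analysis set that is silent on it. That conclusion rests on the stated timing and needs no assumed rate. The 72 hours run from the index procedure, not from randomization; since randomization comes before surgery, the conclusion is the same.

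The size is uncertain and probably modest. Under the assumed differences of 3 to 5 points and OBAS ratios of 1.5 to 2, the shift is about 1.2% to 3.4%, or 0.2 to 0.5 standard errors, against a target reduction of 20%. The direction is unknown, and equal removal gives no shift in this model. A reader might infer that the primary result is seriously biased; the documents do not show this. If the exclusion is applied, what is lost is the randomized comparison itself and the count by arm of chest procedures within 72 hours. Pneumonia and prolonged ventilation would still be recorded, but only in patients who remain.

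**What to change.** 1. Limit criterion 4 to conditions known before randomization, such as redo cardiothoracic surgery.
2. State that a randomized patient who later has a reoperation, tube thoracostomy, thoracentesis or drain placement stays in follow-up and in the primary analysis in the assigned group. Collect OBAS, opioid and, where the patient is able, spirometry data through POD 3.
3. Amend the analysis-set sentence to agree with this for both arms.
4. Add these procedures to the safety outcomes, report them by arm, and include them in the interim safety review.
5. Use exclusion of these patients only as a sensitivity analysis.

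The cost is an amendment to eligibility and analysis wording, continued questionnaires in what is likely to be a small number of patients, slightly more outcome variability and some missing spirometry. The planned 196 for analysis need not change. Nothing here alters patient care.
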